8.4.2. Other Reasons for Discontinuation of Investigational Product

Subjects that discontinue investigational product are expected to continue in the study until the end of the study, and the study will only terminate at the time when the needed number of adjudicated events has accrued or at the discretion of the Sponsor. If a subject reaches an event, he or she should continue the regular visit schedule and continue taking investigational product as long as the Investigator assesses it as safe. Subjects who choose to discontinue investigational product prior to termination of the study need to also continue to follow the regular visit schedule through to study closure. In general, subjects should be strongly encouraged to both stay on investigational product and remain in the study until study termination. Early termination

procedures should only be conducted if the subject withdraws consent (See [Section 9.7.14](#) Early Discontinuation and/or Early Termination Procedures).

The following events are considered appropriate reasons for a subject to discontinue investigational product; however, these subjects are expected to continue in the study until study termination and the study will only terminate at the time when the needed number of adjudicated events has accrued (or at the discretion of the Sponsor):

- The Investigator or Sponsor considers that it is advisable or in the best interest of the subject.
- The occurrence of clinical or laboratory AEs considered by the Investigator to be clinically important.
- Withdrawal of consent
 - Consent may be fully withdrawn
 - Consent may be modified to discontinue study visits but allow semi-annual telephone contact.
 - Consent may be modified to discontinue study visits or semi-annual telephone contact but allow continued access to medical records to assess for potential adjudicated hepatic and/or cardiovascular events.

The Investigator must notify the Sponsor study monitor by telephone or email as soon as possible if any subject prematurely withdraws from the study.

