Early Termination	Discontinued	Withdrawn	No additional visits except EOT/EOS	Combined Visit, Completed as close as possible to last dose IP	
Treatment Discontinuation	Discontinued	Active	Regular Visit Schedule	Complete as close as possible to last dose IP	Complete at Final study visit
	Discontinued	Semiannual contact ^b	Telephone contact every 6 months (± 2 weeks)	Combined Visit, Completed as close as possible to last dose IP	
	Discontinued	Record review only ^b	Record review only	Combined visit Completed as close as possible to last dose IP	
Sponsor Termination	Discontinued	N/A	No additional visits except EOT/EOS	Combined visit Completed as close as possible to last dose IP	
Pregnancy	Interrupted	Retained	Regular Visit Schedule	Complete as close as possible to last dose IP	Complete at Final study visit
	Discontinued	Complete per the above scenarios - Early Termination or Treatment Discontinuation			
Lost to Follow-up	Discontinued	LTF	None	Unable to complete due to LTF status	

EOS = end of study; EOT = end of treatment; IP = investigational product

^a Refer to [Section 7.1.2](#) Schedule of Study Procedures for all procedures and evaluations required at the End of Treatment and End of Study Visits.

^b Outcomes data to be discussed or collected include data related to adjudicated hepatic and cardiovascular event-related data. No additional data (e.g. AE, concomitant medication, etc) data will be collected, except as indicated in [Section 12.1.6](#).

Some assessments noted below may be omitted if they have been completed within the 6 months (or the timeframe otherwise specified) and so long as safety issues do not warrant repeat testing.

Prior to the EOT/EOS Visit:

If possible to do before the visit, when scheduling the EOT/EOS visit, reiterate dosing instructions and advise the subject:

- If applicable, NOT to take investigational product on the morning of the next visit, and
- To bring the investigational product bottle(s); if applicable, s/he will dose at the clinic, and

- To fast overnight (at least 8 hours) prior to the next visit. Fasting is required prior to all study visits, but water is permitted.

During the EOT/EOS Visit:

- Perform a physical examination (including smoking and alcohol consumption habits).
- Assess and record vital signs (height, weight, oral temperature, sitting heart rate, respiratory rate, and sitting blood pressure).
- Perform a standard 12-lead ECG.

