13.1.10.1. Time to Event Endpoints

For the time to event analyses, subjects who do not experience an event will be censored at the time of their last contact. Subjects with no data after randomization will be considered to have an event on Day 1 (first day of investigational product dosing).

For analyses of the percentage of subjects with an event, subjects with no data after randomization will be considered to have an event.

All time to event endpoints include only adjudicated events. Sensitivity analyses may consider all events regardless of adjudication. Events with discrepant adjudication will be analyzed using both results.

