13.4. Adjudication Committee

All potential endpoint events will be reviewed by an adjudication committee before inclusion in the any analysis. The adjudication of potential clinical endpoint events will include, but is not limited to: available hospital reports, histology, discharge summaries, and death certificates. The assessment of events will be conducted in compliance with the protocol, study-specific procedures, manuals, Good Clinical Practice (GCP), and all other applicable regulatory requirements, including the archiving of essential documents. A separate adjudication committee charter will document the entire data flow and process from committee membership, the reporting of events by the study site, reporting of the final assessment, supply of source documentation to the committee, the review of the events by the committee, and the working procedures of the committee. The adjudication committee members will be independent hepatologists not involved in the study as investigators, DSMC members, or consultants. All adjudication committee members will remain blinded to treatment group throughout the study.

In addition to potential clinical endpoint events, cardiovascular events will also be adjudicated. The adjudication of these events will be handled separately from the adjudication of events for assessment of the primary endpoint in this study and will be described separately.

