Individual components of the primary endpoint	As listed above and including liver-related death
Change in baseline liver biochemistry	Liver biochemistry (see Table 5 for list of analytes to be tested)
Inflammation and fibrosis	IgM, C-reactive protein (CRP), tumor necrosis factor-alpha (TNF- α), fibroblast growth factor-19 (FGF-19), cytokeratin-18 (CK-18), enhance liver fibrosis (ELF), and Fibroscan [®]
Clinical outcomes compared to historical controls	Similar endpoints as used for the primary objective where available including liver transplant and death
Pharmacokinetics	OCA and its conjugates
Health outcomes and economics research	Including the following: Cost-effectiveness and resource utilization Quality of life (Fatigue Impact Score and EQ-5D-5L)
Safety and tolerability	Including the following: Treatment-emergent adverse events Clinical laboratory values

Statistical Methods:

Sample Size Justification

The following assumptions were used in sample size calculations:

- Exponential survival curves, placebo survival estimate of 0.5 at 8 years with a hazard ratio of 0.60, and total study duration of 8 years, allowing for 2 years accrual and 6 years of follow up
- Subjects will be randomized in a 1:1 ratio to placebo or OCA.
- The 2 groups will be compared using a 2-sided log rank test at the 5% level of significance

Based on the randomization ratio, significance level, and assumed hazard ratio, a total of 121 events (both groups combined) will provide 80% power to demonstrate a statistically significant difference between OCA and placebo on time to clinical outcomes.

In addition, based on the remaining assumptions stated above, it is estimated that approximately 350 subjects will be enrolled to attain 121 events.

Analysis Populations

The following subject populations will be evaluated and used for presentation and analysis of the data: Randomized, Intent-to-Treat (ITT), Safety, PK, Overall Historical Control, UKPBC Historical Control, and the Global PBS Historical Control. Descriptions of subject populations are provided in [Section 13.1.1](#).

Primary Efficacy Endpoint

The primary efficacy endpoint will be the time to first occurrence of one of the following post-randomization:

- Death (all-cause)
- Liver transplant
- Model of end stage liver disease (MELD) score ≥ 15
- Hospitalization (as defined by a stay of 24 hours or greater) for new onset or recurrence of:
 - Variceal bleed
 - Encephalopathy (as defined by a West Haven score of ≥ 2)

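### The reduced-consent follow-up tiers limit outcome collection to hepatic and cardiovascular events, although all-cause death is part of the primary endpoint, and the telephone tier does not specify record access for adjudication

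*Protocol*

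**What the plan says.** Section 8.4.2 (Amendment 1.1) offers two intermediate options between full participation and full withdrawal of consent.

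- **Telephone tier:** "Consent may be modified to discontinue study visits but allow semi-annual telephone contact".
- **Record-review tier:** visits and calls stop, but the subject may "allow continued access to medical records to assess for potential adjudicated hepatic and/or cardiovascular events".

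Table 2 in Section 9.7.14 lists the two as separate consent states and attaches footnote b to both. The footnote describes the outcomes data as hepatic and cardiovascular event data and adds "No additional data (e.g. AE, concomitant medication, etc) data will be collected", except as Section 12.1.6 indicates. Section 12.1.6 requires serious adverse events arising more than 30 days after drug is stopped to be entered in the data capture system, with their potential endpoint status.

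Sections 6.1 and 13.1.3 make all-cause death a component of the primary composite. Section 13.1.11 tests liver transplant or all-cause death at step 3. Section 13.1.10.1 states "All time to event endpoints include only adjudicated events" and censors event-free subjects at last contact. Section 13.4 gives the adjudication sources as including, without being limited to, "available hospital reports, histology, discharge summaries, and death certificates". Section 11.1.2.4 has the investigator identify potential outcome events from Appendix A, whose only death entry is for liver-related events.

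Section 8.4.2 is quoted from Amendment 1.1. Table 2, Sections 12 and 13 and Appendix A are Amendment 1 text, because the Amendment 1.1 text available stops at Section 9.7.9.

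**The concern.** The two tiers exist to keep outcome information on subjects who will no longer attend visits. Their stated scope should therefore cover at least the clinical events that define the endpoint. As written, the scope names cardiovascular events, which are not components of the composite in their own right, and does not name death from any cause, which is.

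The telephone tier raises a second question. Only adjudicated events count, and adjudication works largely from documents. If a site holds consent for calls alone, it is unclear on what authority it would obtain a discharge summary or death certificate. An event that cannot be documented may not be confirmed, and the subject would then be censored as event-free.

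What is at stake is incomplete ascertainment of the primary endpoint and of key secondary step 3 after visits stop. A later analysis plan cannot recover data that were never collected or consented to.

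**Working it through.** **1. Scope against endpoint.**

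| Event in a reduced-consent tier | Within the stated scope of 8.4.2 and footnote b? | Counts for the primary endpoint? | Route in the text |
|---|---|---|---|
| Hepatic outcome event | Yes | Yes | Direct |
| Non-fatal cardiovascular event | Yes | No (separate adjudication, 13.4) | Direct |
| Liver-related or cardiovascular death | Yes | Yes | Direct |
| Death from cancer, infection or accident | Not named | Yes | 12.1.6 exception only |

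The last row is the gap. Section 12.1.1.2 makes an adverse event that results in death serious, so Section 12.1.6 applies once the site knows of the death. The weak links are that the site must learn of it, that Section 8.4.2 does not mention this route, and that Appendix A does not prompt the site to flag a non-liver death as a potential endpoint.

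**2. The plan's own figures.** The Synopsis states "a total of 121 events (both groups combined) will provide 80% power", with "The 2 groups will be compared using a 2-sided log rank test at the 5% level of significance" and "placebo survival estimate of 0.5 at 8 years with a hazard ratio of 0.60, and total study duration of 8 years". The Schoenfeld formula with 1:1 allocation gives

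4 × (1.960 + 0.842)² / (ln 0.60)² = 120.3, rounded up to 121, with power 0.802 at 121 events.

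The stated figure is reproduced. For the sample size, the placebo hazard is ln 2 / 8 = 0.0866 per year and the OCA hazard is 0.60 × 0.0866 = 0.0520. With uniform accrual over 2 years and 6 further years of follow-up, the event probabilities are 0.454 and 0.305, mean 0.379. Then 121 / 0.379 is about 319 subjects, and 350 subjects give about 132.8 expected events. The surplus is about 12 events.

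**3. Deaths outside the named scope (illustration).** Assume 35 to 70 subjects (10% to 20% of 350) spend 3 years in the tiers, with mortality from other causes of 0.5% to 1.5% per year. None of these figures is in the protocol.

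- Low: 35 × 3 × 0.005 = 0.5 deaths.
- High: 70 × 3 × 0.015 = 3.2 deaths.

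These counts are before the Section 12.1.6 route recovers any.

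**4. Effect on the hazard ratio (illustration).** Assume further that half of all events in the tiers go unconfirmed, which is severe because one tier consists of record access. The 121 events split as about 48.6 OCA and 72.4 placebo (in proportion to 0.305 and 0.454). Events lost per arm = subjects in the tiers × 3 × arm hazard × 0.5. The hazard ratio is multiplied by (1 − OCA lost / 48.6) / (1 − placebo lost / 72.4).

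| OCA:placebo split in the tiers | 35 subjects: lost OCA / placebo | HR shift | 70 subjects: lost OCA / placebo | HR shift |
|---|---|---|---|---|
| 2:1 | 1.8 / 1.5 | −1.7% | 3.6 / 3.0 | −3.4% |
| 1:1 | 1.4 / 2.3 | +0.3% | 2.7 / 4.5 | +0.7% |
| 1:2 | 0.9 / 3.0 | +2.4% | 1.8 / 6.1 | +5.1% |

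The sign depends on the assumed split. The standard error of the log hazard ratio at 121 events is about 2 / √121 = 0.18, so even the largest shift shown (log 1.051 = 0.049) is about 0.27 standard errors.

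**5. Power.** If 3% of subjects moved to these tiers each year and every later event were lost, 350 subjects would still give 120.6 events by year 8 (power 0.801). At 5% per year the figures are 113.2 events and 0.776. Because the trial runs until about 121 adjudicated events, such losses would mainly lengthen it.

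**The case against.** The strongest reply is that the gap is one of wording. Three stronger readings that a reader might infer are not supported.

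- **Other-cause deaths cannot be captured.** They can, through Section 12.1.6, which records outcome and potential endpoint status for any fatal serious adverse event the site learns of. It can also be argued that hepatic and cardiovascular simply names the two adjudication streams in Section 13.4, since Section 13.1.2 describes the primary outcome as liver-related outcomes including all-cause mortality. Appendix A, with its liver-only death entry, points the other way. The text is therefore ambiguous, and the available route is indirect.
- **The telephone tier denies record access.** It is silent. The next tier speaks of continued access to records, which may imply that telephone subjects keep it. Section 12.1.5 separately asks investigators for discharge summaries and autopsy reports on serious adverse events, and the supply of source documents is left to a charter that is not shown. The supportable statement is that access is unspecified.
- **The hazard ratio is biased in favour of OCA.** Pruritus (Section 5.6) could move OCA subjects into the tiers, but Section 5.5.2.2 names commercial OCA as a possible source of bias associated with the placebo arm. The protocol gives no rates, and the illustration changes sign with the split.

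Section 13.1.10.1 also allows a sensitivity analysis of events regardless of adjudication, but it is optional and cannot include events that were never collected.

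Finally, the tiers retain subjects who might otherwise withdraw entirely, and a wider request may be declined. That is a real cost. A subject's right to limit consent is not in question here. What stands is that the scope offered to subjects still willing to be followed is narrower than the endpoint.

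**Conclusion.** The point holds as a defect in the stated scope of data collection. Section 8.4.2 and footnote b name hepatic and cardiovascular events, while the primary composite and key secondary step 3 count death from any cause. The only route for other deaths is indirect and is absent from the consent wording. Record access for adjudicating telephone-reported events is unspecified.

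The size is unknown. Under the assumptions shown, about 0.5 to 3 deaths fall outside the named scope, and hazard ratio shifts are a few percent in either direction. These figures illustrate scale and do not estimate bias. The 121-event target and the 80% power stand as stated. The conclusion also assumes that Amendment 1.1 left footnote b, Section 12.1.6 and Appendix A as they read in Amendment 1. This is a cheap improvement worth making, and it does not challenge the validity of the primary analysis.

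**What to change.** In Section 8.4.2, Table 2 footnote b and the consent addendum required by Section 9.7.2, state for both tiers that:

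- vital status, with the date and cause of any death, is collected;
- liver transplant and potential hepatic and cardiovascular outcome events are collected;
- the records needed to adjudicate any reported event may be obtained.

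Align Appendix A so that death from any cause is listed as a potential outcome event for adjudication. Appendix A also defines events that may be exempt from expedited regulatory reporting, so the added entry should be marked as applying to adjudication only. Otherwise the change would widen that exemption unintentionally.

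The cost is amendment and consent wording, ethics review of the addendum, and a few more record requests. Some subjects may decline the wider scope. Presenting its elements as separate choices in the addendum would let a subject who refuses record release still agree to vital status.

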8.4.2.1. Withdrawal of Consent

If the subject decides that it is in his/her best interest to discontinue from the study, he or she may withdraw consent. It is fully understood that all subjects volunteer for the study and that they may withdraw their consent to continue in the study at any time.

A reasonable effort must be made to determine the reason(s) for subject discontinuation. This information and date must be recorded in the appropriate case report form (CRF).

8.4.2.2. Lost to Follow-up

If a subject fails to return to the clinic for a study visit, and the Investigator ceases to have contact with the subject, he or she will be withdrawn from the study.

A reasonable effort must be made to contact the subject and determine the reason(s) why a subject fails to return for a study visit or is lost to follow-up. This information and date of contact must be recorded in the appropriate CRF.

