8.4.3. Subject Discontinuation Notification

The Investigator must notify the Sponsor study monitor by telephone or email as soon as possible if any subject prematurely withdraws from the study. The date when the subject is withdrawn and the reason for discontinuation must be recorded in the CRF. If a subject is “lost to follow up” (fails to return for a visit), a reasonable effort should be made to contact the subject in order to determine why the subject failed to return. This information must be documented in

the CRF. If a subject is withdrawn from the study early (regardless of the cause), all of the EOT/EOS evaluations should be performed at the time of withdrawal, as appropriate (See [Section 9.7.14](#) Early Discontinuation and/or Early Termination Procedures).

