9.7.2. Informed Consent Procedures

The Investigator or designee will explain the nature, purpose, possible risk and benefit of the study to the subject and will provide him/her with a copy of the written information and informed consent form (ICF). The subject will be given sufficient time to consider the study before deciding whether or not to participate. The subject will be informed that participation is voluntary and that her/his future medical treatment will not be compromised by participation in the study and that s/he can withdraw from the study at any time. The subject must be willing and able to provide written informed consent before entering the study. The Investigator or a medically qualified designee is responsible for administering and documenting the written informed consent of the subject. The subject will be given a copy of the written information and his/her signed and dated consent form.

Any change in a subject's consent status (eg, semi-annual telephone contact or medical record review) must be documented in a signed informed consent form or addendum. The subject will be given a signed and dated copy of the consent document.

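### The lost-to-follow-up rule withdraws subjects who cannot be reached and asks for no vital-status or transplant check, so a death or transplant that stays undiscovered is censored at last contact

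*Protocol*

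**What the plan says.** Section 8.4.2.2 (Amendment 1.1) applies when a subject does not come to a visit "and the Investigator ceases to have contact with the subject, he or she will be withdrawn from the study". It then sets the effort required: "A reasonable effort must be made to contact the subject and determine the reason(s) why a subject fails to return for a study visit". Section 8.4.3 repeats this for anyone lost to follow-up: "a reasonable effort should be made to contact the subject in order to determine why the subject failed to return". Both want the findings recorded in the CRF. Neither names a source other than the subject, or a question other than why the visit was missed.

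Follow-up without visits does exist. Section 8.4.2 lets a subject modify consent so as to keep six-monthly telephone contact, or to "allow continued access to medical records to assess for potential adjudicated hepatic and/or cardiovascular events". Under Section 9.7.2, any change in consent status "must be documented in a signed informed consent form or addendum".

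Table 2 in Section 9.7.14 has rows for these telephone and record-review options. Its Lost to Follow-up row gives the study visit status as None, and for the closing visits says "Unable to complete due to LTF status".

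For analysis, Section 13.1.10.1 states that "subjects who do not experience an event will be censored at the time of their last contact". Section 13.1.10 assumes that missing data are missing at random.

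On versions: the Amendment 1.1 text supplied ends at the heading of Section 9.7.9. Sections 8.4.2 to 8.4.3 and 9.7.2 are quoted from it. Table 2 and Section 13.1.10 are quoted from Amendment 1. The October 2014 protocol has the same censoring rule, and the contents list of Amendment 1.1 still includes Table 2 and Section 13.1.10.1.

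**The concern.** All-cause death and liver transplant are components of the primary endpoint, and together they form the second key secondary endpoint. Both can be established without speaking to the subject. In this population either one is a plausible reason for a subject to fall silent. Trying to reach the subject is the effort least likely to reveal that the subject has died.

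The protocol elsewhere wants subjects followed to study close even when off drug or after an event. It also has a way to collect outcomes from subjects who refuse visits. A subject who declines visits and signs can still contribute outcomes; one who simply disappears leaves the study. Where the reason for disappearing was a death or transplant nobody learned of, the outcome itself caused the censoring, and the missing-at-random assumption fails for that subject. This is a data-collection rule, so no later analysis plan can recover outcomes that nobody sought.

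**Working it through.** **1. The protocol's own event target.** Inputs from Section 13.1.2 and the synopsis: hazard ratio 0.60, two-sided 5%, 80% power, 1:1 allocation. By Schoenfeld's formula, events = 4 × (1.960 + 0.842)² / (ln 0.60)² = 31.40 / 0.2609 = 120.3, rounded up to 121. The stated figure reproduces, and nothing in this point depends on changing it.

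**2. Event hazards.** Placebo event-free probability is 0.5 at 8 years, exponential: λP = ln 2 / 8 = 0.0866 per year, and λO = 0.60 × 0.0866 = 0.0520. Two years' accrual plus six years' follow-up is taken as follow-up t uniform between 6 and 8 years. Without loss, the event probabilities are 0.454 (placebo) and 0.305 (OCA), mean 0.379, so 350 × 0.379 = 132.8 expected events.

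**3. Subjects lost before an event.** The protocol states no loss rate, so the rate g is an assumption. For each arm,

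P(lost first) = g / (λ + g) × (1 − exp(−(λ + g)t)), averaged over t.

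Example at g = 0.02, using t = 7:
- placebo: 0.1876 × (1 − exp(−0.746)) = 0.099
- OCA: 0.2778 × (1 − exp(−0.504)) = 0.110
- mean 0.104, times 350 = about 36.5

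| Assumed loss per year | Lost before an event | Expected composite events observed | Fall from 132.8 |
|---|---|---|---|
| 1% | 18.8 | 128.6 | 4.2 |
| 2% | 36.5 | 124.6 | 8.2 |
| 3% | 53.0 | 120.8 | 12.0 |

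**4. What the table measures.** The second column is the number of subjects to whom the rule would apply. The last column is not a count of hidden deaths and transplants. It covers all composite events after loss, including MELD ≥15, ascites, carcinoma and hospitalizations, and it assumes that loss is unrelated to outcome. Under that assumption the hazard ratio is not biased and the cost is time to 121 events.

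**5. Undiscovered deaths and transplants.** The documents give no share. If 10% to 50% of lost subjects had one (assumed), the number runs from about 2 (10% of 18.8) to about 27 (50% of 53.0).

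**6. How much imbalance would matter.** At 121 events and an observed hazard ratio of 0.60, the expected split is 72.4 placebo and 48.6 OCA. A net excess of 9 hidden events in the OCA arm would move the ratio to 0.60 × (48.6 + 9) / 48.6 = 0.71, and p from 0.005 to about 0.052. An excess in the placebo arm would move it the other way. Nothing in the documents says which is likelier.

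**The case against.** The strongest answer is that the protocol is not silent. Sections 8.4.2.2 and 8.4.3 require a reasonable effort to determine why contact was lost, and a death or transplant would be that reason. Once known, it can be adjudicated: Section 13.4 lists death certificates and hospital reports among the sources, and Section 12.1.6 still wants late serious events entered with their potential endpoint status. This stands. A reader might infer that every death or transplant behind a silence is censored; only those still undiscovered after that effort are. Section 13.1.10.1 also counts a subject with no data after randomization as having an event on Day 1, so that group is not censored at all.

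Three further inferences are tempting and not supported.
- **That 4 to 12 events measure the bias.** They are composite events under non-informative loss.
- **That loss would differ by arm through pruritus.** Section 5.6 names pruritus as the main related adverse event, but no passage links it to loss of contact. The protocol allows dose reduction and interruption for tolerability, and continued visits off drug.
- **That the baseline consent forbids a look-up.** Consent pages are not in the material, and Section 16.4 (Amendment 1) foresees access to hospital records for data verification. Section 9.7.2 shows only that a change of consent status needs a signature.

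What remains is that no passage tells a site to establish vital or transplant status for a lost subject, and that the one table covering the case assigns no follow-up.

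**Conclusion.** The point holds in a limited form. The rule withdraws subjects who cannot be reached and asks for no vital-status or transplant check, so undiscovered deaths and transplants are censored at last contact. Such censoring can be informative for the primary endpoint and for the second key secondary endpoint.

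The size and direction of any effect on the hazard ratio are unknown. At an assumed 1% to 3% loss per year, with the protocol's own event hazards and uniform accrual, the rule would reach about 19 to 53 of 350 subjects. No stated figure in the protocol is wrong. The change is worth making because the gap is in data collection and cheap to close. The conclusion assumes that Table 2 and Section 13.1.10.1 carry over unchanged into Amendment 1.1, whose later pages are not shown.

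**What to change.** 1. **Section 8.4.2.2.** Replace withdrawal with continued outcome follow-up. Possible wording: *A subject who misses visits and cannot be contacted remains in outcome follow-up. Before the subject is classed as lost, and again at study close, the site ascertains vital status (with date and cause of death) and liver transplant from medical records, the usual-care physician and public registries, where consent and local law permit.* Align Section 8.4.3.
2. **Consent.** Include this permission in the baseline consent, so that no later signature is needed.
3. **Table 2.** In the Lost to Follow-up row, change the visit status from None to record/vital-status review, after checking the row in the current amendment.
4. **Section 13.1.10.1.** State that deaths and transplants found this way count as events. For the composite endpoint, a lost subject with neither found stays censored at last contact, because MELD and the other components were not assessed after that date.

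The change needs no new rule on investigational product and should not add one.

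The cost is protocol and consent wording plus a small number of look-ups: a few dozen subjects, each checked twice, at the assumed loss rates. Privacy law will prevent the look-up in some countries, so ascertainment will be incomplete, and the number of subjects with unknown vital status at close should be reported by arm.
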